Although there is no perfect method for estimating a causal effect in observational data (10), conceptual frameworks exist to guide the design and analysis of observational studies in order to limit apparent paradoxes and common biases and increase the transportability of estimates (3,11). In fact, causal inference from observational databases can be viewed as an attempt to emulate a randomised experiment (the "Target Trial") to answer the question of interest (3). In this study, the effectiveness of SARS-CoV-2 primary vaccination in preventing SARS-CoV-2 infection is assessed across national borders, using a framework for causal inference. The well-defined causal analysis methodology will subsequently be deployed across federations to reproduce the analysis and pool the aggregated results. We aim to inform high-level vaccine policy by leveraging real-world observational data from multiple data sources hosted in multiple sites (i.e., countries).

Research guestion/objectives

We aim to investigate the real-world effectiveness of SARS-CoV-2 primary vaccination as compared to partial or no vaccination in preventing SARS-CoV-2 infection in virtually all resident populations spanning different countries. The study will be conducted in two sequential stages, expanding the exercise to several countries/regions:

- Stage I (pilot): Aragon (Spain) and Belgium.
- Stage II: Aragon (Spain), Belgium, Austria, Finland, Norway, Estonia and The Netherlands. The participation of these countries/regions is conditional on data access.

Methodology

Study design and context

The study design is an observational retrospective longitudinal (cohort) study using routinely collected administrative, social, health and care data from several

countries/regions in Europe. We have designed the observational study to emulate a hypothetical Target Trial (TT) of the causal effect of SARS-CoV-2 vaccination programmes in preventing SARS-CoV-2 infections.

Target Trial specification and emulation

The key components of the target trial and its subsequent emulation are explicitly described in Table 1. Several of the key components are part of the widespread population, intervention, control, and outcome (PICO) approach to the formulation of clinical questions (12).

Protocol Component	Target Trial Specification (Ideal Hypothetical Trial)	Target Trial Emulation (Actual Study Design reusing Real World Data)

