Eligibility criteria	 Study population: All individuals eligible to be vaccinated. Enrollment period: From the start of the SARS-CoV-2 vaccination campaign (January 1, 2021) to the start of the SARS-CoV-2 booster vaccination campaign (September 1, 2021). Age: 5 to 115 years old, included (all individuals eligible to be vaccinated). Previous infection: Individuals without a SARS-CoV-2 infection before enrolment. Country: Individuals living in the respective country 	 Study population: All individuals vaccinated with at least one dose of the SARS-CoV-2 vaccine (any of the available brands) and all individuals eligible to be vaccinated with a documented positive diagnosis (irrespective of the type of test) for SARS-CoV-2 infection during the data extraction period. Enrollment period: From the start of the SARS-CoV-2 vaccination campaign (January 1, 2021) until the start of the SARS-CoV-2 booster vaccination campaign (September 1, 2021). Age: 5 to 115 years old, included (all individuals eligible to be vaccinated). Previous infection: Individuals without a documented confirmed infection before completing the primary vaccination schedule (i.e. enrolment) or before January 1, 2021 (SARS-CoV-2 vaccine roll-out) for those not having completed a primary vaccination schedule (controls). Country: Resident of the registered individuals in the COVID-19 cases and vaccination datasets. Individuals with neither a registered vaccine dose nor a positive diagnosis during the data extraction period are therefore excluded.
Treatment strategies	 Primary analysis Completing a primary vaccination schedule (from any vaccine brand) Not completing a primary vaccination schedule (either not receiving a vaccine or being only partially vaccinated). Secondary analysis Completing a homogeneous primary vaccination schedule with 	Same as in Target Trial Specification. Vaccination status ascertainment (including brand, dose and date) based on the vaccination registry. Date of being primary vaccinated (completing a primary vaccination schedule) is considered as 14 days after receiving the final dose of the primary vaccination schedule (one dose for the Johnson-Johnson vaccine and two doses of any of the other vaccines considered).

Table 1. Protocol of the target randomised control trial and target trial emulation by using observational data.

Funded by

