BY-COVID is funded by the European Union's Horizon Europe research the European Union and innovation programme under grant agreement number 101046203.

4

Funded by the European Union

	a specific brand (BioNTech-Pfizer, Moderna, Johnson-Johnson, Astrazeneca, Novavax) 2) Not completing a primary vaccination schedule (either not receiving a vaccine or being only partially vaccinated). Pragmatic trial: strategies compared under the usual conditions.	
Assignment procedures	Participants will be randomly assigned, at baseline, to either completing the primary vaccination schedule or to not completing the primary vaccination schedule (no or only partial vaccination). The participants will be aware of the strategy to which they have been assigned (i.e., without blind assignment).	To mimic randomization, we need to adjust for all confounding factors required to ensure comparability (conditional exchangeability) of the groups defined by vaccination (as identified in the Directed Acyclic Graph (13)). We assume that individuals are randomly assigned within levels of baseline covariates: Age, Gender, Comorbidities, ImmuneStatus, EssentialWorker, Foreign, Institutionalised people, Pregnancy, and ResidenceArea. The adjustment will be performed via matching.

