Follow-up period	 Starts, for each individual, at randomization to one of the vaccination strategies (baseline) Ends at diagnosis of SARS-CoV-2 infection (i.e., outcome of interest), death, loss to follow-up, the date of receiving a booster dose, 168 days after baseline (24 weeks), or the end of the study period (March 1, 2022), whichever occurs first. 	 Sequential trial emulation: Starts, for each individual: Vaccine group: time of completing a primary vaccination schedule No (or partial) vaccine group: first eligible time (time of completing a primary vaccination schedule of the matched pair) Ends at diagnosis of SARS-CoV-2 infection, death (all causes), vaccination (for unvaccinated controls), completed primary vaccination of the matched control (for vaccinated persons), booster dose (for vaccinated persons), booster dose of the matched vaccinated persons), booster dose of the matched vaccinated person (for unvaccinated controls), or the end of the study period (i.e., the most recent date at which data is available at time of analysis). Loss to follow-up due to emigration or 'disenrollment' from the health care system not taken into account. Newly vaccinated individuals (completing a primary vaccination schedule) are eligible for inclusion in the "vaccine group" of the study, even if they had previously been selected in the "no vaccine group" (as controls).
Outcome	Laboratory-confirmed SARS-CoV-2 infection	A documented laboratory-confirmed SARS-CoV-2 infection, thus excluding self-reported test results
Causal contrast of interest	Per-protocol effect.	Observational analog of the per-protocol effect.

In the target trial (Figure 1), eligible participants are enrolled from January 1, 2021 (start of the SARS-CoV-2 vaccination campaign) until September 1, 2021 (start of the SARS-CoV-2 booster vaccination campaign). As such, the enrolment period in the target trial covers a

Funded by the European Union period of 9 months. For each eligible participant, follow-up starts at the moment of randomisation (baseline, t_0) and ends at diagnosis of SARS-CoV-2 infection (outcome of interest), death, loss to follow-up, receiving a booster dose, or 6 months after baseline. The period of data collection runs until March 1, 2022 to allow for a minimal follow-up period of 6 months for those participants with baseline (t_0) at the end of the enrollment period.

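### Table 1 starts the clock at randomisation in the target trial but 14 days after the final dose in the emulation, so the hazard ratio answers a narrower question than the one it is labelled with

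*Protocol*

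**What the plan says.** **Target trial.** Table 1 (Assignment procedures) states: "Participants will be randomly assigned, at baseline, to either completing the primary vaccination schedule or to not completing the primary vaccination schedule". The Follow-up row says that follow-up "Starts, for each individual, at randomization to one of the vaccination strategies (baseline"), and the text below the table repeats it: "For each eligible participant, follow-up starts at the moment of randomisation (baseline, t_0"). Eligibility requires no infection before enrolment. Follow-up is capped at 168 days.

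**Emulation.** The Follow-up row gives, for the vaccinated, "Vaccine group: time of completing a primary vaccination schedule", and for controls "first eligible time (time of completing a primary vaccination schedule of the matched pair"). The Treatment strategies row says that the date of completion "is considered as 14 days after receiving the final dose of the primary vaccination schedule". The previous-infection criterion admits "Individuals without a documented confirmed infection before completing the primary vaccination schedule (i.e. enrolment") and, for those who have not completed, applies a cut-off of 1 January 2021. The Participants section repeats this. Anyone who has not yet completed the schedule, including the partly vaccinated, can be matched as a control.

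**Labels.** The Treatment strategies row declares the strategies identical to those of the target trial. The Causal contrast row calls the result the observational counterpart of the per-protocol effect. Study design and context describes a target trial of the "causal effect of SARS-CoV-2 vaccination programmes in preventing SARS-CoV-2 infections". The formal objective, under the research question, is narrower: primary vaccination against partial or no vaccination.

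**The concern.** The protocol rests its causal claim on emulating a specified target trial. For that claim to hold, eligibility, assignment and start of follow-up must correspond between the two columns, and here they do not.

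In the target trial, completing a schedule is something a participant does after randomisation. Infections during dosing, between doses and in the first 14 days after the last dose are outcome events in the arm assigned to vaccination. In the emulation, the same infections keep a person out of the vaccine group. No passage says that time zero has moved, or that the result applies only from day 14 after the final dose in people uninfected until then.

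The protocol aims to inform high-level vaccine policy. A reader who trusts the target column could take the pooled HR as the benefit of entering a vaccination programme, when it is the benefit seen once the schedule is complete and the 14 days have passed.

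**Working it through.** The protocol states no sample size, effect size or expected HR, so there is no figure of its own to reproduce. The check is a comparison of the columns, followed by an illustration.

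**Step 1. The two columns side by side**

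| Component | Target trial | Emulation |
|---|---|---|
| Time zero, vaccinated | Randomisation | 14 days after the final dose |
| Time zero, controls | Randomisation | Matched vaccinated person's completion date |
| Infection-free until | Enrolment (randomisation) | Vaccinated: completion. Controls, as worded: 1 January 2021 |
| Infection in build-up, vaccine group | Outcome event | Bars entry to that group |

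**Step 2. Can the columns be read as the same?** They would agree if randomisation in the target trial took place at completion. But a person 14 days past the final dose cannot be assigned to not completing. The specified assignment makes sense only if it precedes completion, so the build-up lies inside target follow-up.

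**Step 3. What happens to infections in build-up?** They cannot be vaccine-group events. They can be control events: someone between doses, or within 14 days of the last dose, has not yet completed and may be serving as a control. How many count is unclear. Table 1 ends a control's follow-up at vaccination, while the text under Figure 2's description and the Statistical analysis plan section end it at completed primary vaccination.

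**Step 4. Is immortal time counted?** No. Both members of a pair start on the same calendar date, and vaccine-group person-time before that date is not counted.

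**Step 5. Illustration of size.** Inputs from the protocol: the 14-day lag, the 168-day target follow-up, and one-dose and two-dose schedules. Assumed, because the protocol gives none of them: dose interval G, HR during build-up h_b, HR afterwards h_p, a constant control hazard and low incidence. The build-up is B = G + 14 days, and

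average HR from randomisation = [B × h_b + (168 − B) × h_p] / 168.

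With h_p = 0.15, which is what the emulation would report:

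- One dose, B = 14: h_b = 0.5 gives (7.0 + 23.1)/168 = 0.18; h_b = 1 gives (14.0 + 23.1)/168 = 0.22.
- Two doses, G = 21, B = 35: h_b = 0.5 gives (17.5 + 19.95)/168 = 0.22; h_b = 1 gives (35.0 + 19.95)/168 = 0.33.

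With h_p = 0.30, the emulated effectiveness of 70% becomes 64% to 68% for B = 14 and 55% to 66% for B = 35, as h_b goes from 1 to 0.5. The answer depends heavily on G: with G = 84 (B = 98) and h_p = 0.15, the same formula gives (49.0 + 10.5)/168 = 0.35 to (98.0 + 10.5)/168 = 0.65. When h_b = h_p the formula returns h_p and there is no gap. The documented 14 days alone are 14/168 = 8.3% of the target follow-up.

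**The case against.** The best defence is that nothing is concealed. The 14-day rule and the prior-infection exclusion stand openly in the emulation column, and the exclusion is repeated under Participants. The formal objective compares primary with partial or no vaccination, which is a contrast by completion status that the emulation does address. Pairs start on a common date, so the HR is a coherent measure of effectiveness from day 14, provided that controls are also uninfected at that date. The target column gives no date for the first dose and may simply be loosely worded. Figures 1 and 2 were not available for this check.

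Most of this stands. It limits the point to the mismatch and the label, and it does not make the HR unusable. What does not stand is the loose-wording defence, because assignment to not completing is impossible once the schedule is complete. The stated rules also do not declare their own consequence for time zero.

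A reader might infer three stronger things that the documents do not support:

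- **Immortal-time bias in the vaccine group.** The shared start date rules this out.
- **Infections during build-up vanish from the study.** They leave the vaccine group, but some can be counted as control events.
- **A known, large overstatement.** Dose interval and both HRs are assumed, the one-dose schedule gives only a small gap, and the emulation has no 168-day cap, so the 168-day average is only a yardstick.

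**Conclusion.** The point holds as a mismatch between the specified and the emulated estimand. The HR estimates effectiveness from 14 days after the final dose in people uninfected until then. It does not estimate the target trial's per-protocol effect from randomisation, and it does not support a statement about vaccination programmes.

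The direction is conditional: the emulated HR is the more favourable if protection is weaker during build-up than afterwards. The size cannot be found from the protocol. Under the stated assumptions, an emulated HR of 0.15 corresponds to about 0.18 to 0.22 from randomisation for a one-dose schedule, and 0.22 to 0.33 for two doses 21 days apart. The calculation leaves out build-up infections counted among controls, which could widen the emulated contrast further.

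The primary analysis can stay as it is. The description should be changed, because it decides what may be concluded.

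**What to change.** **Align Table 1.** Keep assignment before dosing in the target trial, since nobody can be assigned after completing. Declare in both columns that outcomes count only from 14 days after the final dose, at the pair's common date, among people uninfected until that date in both arms.

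**Name the estimand.** In the design sentence under Study design and context, in the Causal contrast row and in the reported conclusion, write: effectiveness from 14 days after completing the schedule, in people uninfected until then. The cost is redrafting only.

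**Then choose.** Either drop the programme-effect wording or, if that effect is to be claimed, add a secondary sequential emulation with time zero at the first dose that counts all infections from that date. The vaccination registry already holds the dose dates. The cost is new matching and censoring rules at each site and a probably less favourable estimate.

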In the sequential emulated target trial (Figure 2), each eligible individual is considered as a different individual at each eligible time (i.e., *daily*). As such, a sequence of nested (*daily*) trials are emulated with increasing time $(t_1, t_2, ..., t_n)$, iterating over the days in the enrollment period. At each eligible time during the enrollment period, the vaccination status of eligible individuals is assessed and every individual who has completed a primary vaccination schedule at that time (treated/exposed) is matched to an individual who has not (yet) completed the primary vaccination schedule (control). Newly vaccinated individuals (completing a primary vaccination schedule) are eligible for inclusion in the study, even if they had previously been selected in the "no (or partial) vaccine group". Follow-up ends at diagnosis of SARS-CoV-2 infection, death, death of matched person, completed primary vaccination (for unvaccinated or partially vaccinated controls), completed primary vaccination of the matched control (for primary vaccinated persons), booster dose (for primary vaccinated persons), booster dose of the matched vaccinated person (for unvaccinated or partially vaccinated controls), or the end of the study period. The study period ends at the most recent date at which data is available at the time of analysis. The data extraction period starts from the date of the first documented SARS-CoV-2 infection, in order to appropriately identify individuals with a previously documented SARS-CoV-2 infection.

[figure not shown]

Figure 1. Timeline of the target trial (ideal hypothetical trial).

BY-COVID is funded by the European Union's Horizon Europe research the European Union and innovation programme under grant agreement number 101046203.

[figure not shown]

Figure 2. Timeline of the sequential emulated target trial (actual study design reusing Real World Data).

BY-COVID is funded by the European Union's Horizon Europe research the European Union and innovation programme under grant agreement number 101046203.

Sources of information

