For each person, follow-up ends at the occurrence of the outcome event (i.e., a confirmed SARS-CoV-2 infection), death (all causes), completing primary vaccination (for unvaccinated or partially vaccinated controls), completing primary vaccination of the matched control (for vaccinated persons), vaccination with a booster dose (for vaccinated persons), vaccination with a booster dose of the matched vaccinated person (for unvaccinated or partially vaccinated controls), or the end of the study period (i.e., the most

BY-COVID is funded by the European Union's Horizon Europe research the European Union and innovation programme under grant agreement number 101046203.

recent date at which data is available at time of analysis). Newly vaccinated persons (completing a primary vaccination schedule) are eligible for inclusion in the study, even if they have previously been selected as a control. As such, the matched controls enrolled at a particular day during the enrollment period are those who are unvaccinated (or partially vaccinated) at this date but may receive a first (or second) vaccination dose at a later date during the data extraction period.

Differences in the occurrence of a SARS-CoV-2 infection (as a time-to-event outcome) between primary vaccinated and unvaccinated or partially vaccinated individuals (average treatment effect, ATE (16)) will be computed by using adjusted Cox proportional-hazards models (17), and hazard ratios (HRs) and a robust variance estimate will be obtained.

A secondary analysis will be performed where the effectiveness of primary vaccination in preventing SARS-CoV-2 infection is assessed for different vaccine brands (e.g. BioNTech-Pfizer, Moderna, Johnson-Johnson, Astrazeneca, Novavax), hence conducting a stratified analysis using the matched pairs constructed for the primary analysis. Further, we can assess vaccine effectiveness during different time periods, with a dominant circulation of different SARS-CoV-2 variants.

Several sensitivity analyses will be performed accounting for different imputation algorithms, and different matching algorithms and compared in covariate balance after matching, robustness of the survival estimate and computing efficiency of the algorithm.

HRs and variance estimates will be collected from each country or region, and a meta-analysis will be performed in which the HRs are pooled by using the inverse variance method (18).

Ethical aspects

Balance risk/benefit

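### The three end-of-follow-up lists disagree on when a control and its vaccinated partner are censored, and the 14-day completion rule admits fully dosed people as controls

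*Protocol*

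**What the plan says.** All places are in the Protocol.

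- **Table 1, Follow-up period, emulation column.** The vaccination-related ends of follow-up are "vaccination (for unvaccinated controls), completed primary vaccination of the matched control (for vaccinated persons". Partially vaccinated controls get no vaccination-related end. Death of the person is listed; death of the matched person is not.
- **Target Trial specification and emulation, paragraph on the sequential emulated trial.** The ends are "completed primary vaccination (for unvaccinated or partially vaccinated controls), completed primary vaccination of the matched control (for primary vaccinated persons". Here the list opens with "death, death of matched person, completed primary vaccination (for unvaccinated or partially vaccinated controls", so the partner's death also ends follow-up.
- **Statistical analysis plan section.** Follow-up of controls ends on "completing primary vaccination (for unvaccinated or partially vaccinated controls", and the partner is censored at the same event. The partner's death is not listed.
- **Table 1, Treatment strategies.** The date of completion "is considered as 14 days after receiving the final dose of the primary vaccination schedule", with "one dose for the Johnson-Johnson vaccine and two doses of any of the other vaccines considered". The comparator is "Not completing a primary vaccination schedule (either not receiving a vaccine or being only partially vaccinated".
- **Choice of control (same paragraph on the sequential emulation).** Each newly completed person "is matched to an individual who has not (yet) completed the primary vaccination schedule (control".

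**The concern.** These lists decide which person-time counts in the primary per-protocol contrast.

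First, the control's vaccination-related end is worded differently in the table and in the text. If the table is taken at its word, a control leaves at a dose while its partner stays until the control's completion. The pair was matched on a calendar day so that both members would face the same epidemic. The partner's extra time has no counterpart, and the protocol does not say that the Cox model is stratified by pair, which would remove that time. The partner-death rule has a similar gap: it appears in one list of three.

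Second, the 14-day lag is a sensible entry rule for the vaccine group, but the same date also defines who is still a control. Someone with the full schedule is neither unvaccinated nor only partially vaccinated, yet for 14 days counts as not completed. On a one-dose schedule there is no partial state at all. If such people are already partly protected, they lower the infection rate in the comparator and shrink the estimated effect.

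**Working it through.** The protocol states no sample size, event count, dose interval or assumed hazard ratio, so there is no figure to reproduce. The rules can be compared directly. The sizes below rest on assumed inputs.

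**Step 1. The rules side by side**

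| Place | Control's vaccination-related end | Partner's matching end | Partner's death |
|---|---|---|---|
| Table 1 | *vaccination*, for unvaccinated controls only | control's completion | not listed |
| Design text | completion, unvaccinated or partially vaccinated | control's completion | listed |
| Statistical analysis plan section | completion, unvaccinated or partially vaccinated | control's completion | not listed |

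**Step 2. Unpaired time if Table 1 is read literally** (*vaccination* = first dose)

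Extra partner follow-up = dose interval + 14 days.

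- One-dose schedule: 0 + 14 = 14 days.
- Assumed intervals of 21, 28 and 84 days: 35, 42 and 98 days.
- Under the two text lists: 0 days.

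**Step 3. Fully dosed people in the control group**

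Completion = final dose + 14 days, and a control is anyone not yet completed. A person is therefore selectable as a control on days 0 to 13 after the final dose. Under the two text lists that person stays in follow-up as a control until day 14. Table 1's literal rule would stop this for a control who was unvaccinated at matching, but it does not stop selection of someone already fully dosed.

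**Step 4. How much time this could be (assumed roll-out)**

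Final-dose dates are uniform up to day 243 (1 January to 1 September 2021). The control is drawn at random from those not yet completed. Follow-up runs to the control's completion or to day 423 (243 + 180), with no infection, death or booster modelled.

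| Never vaccinated | Dose interval (days) | Control person-time in the window | Controls fully dosed at matching |
|---|---|---|---|
| 8% | 21 | 10.8% | 12.9% |
| 8% | 84 | 12.9% | 17.4% |
| 20% | 21 | 5.9% | 9.5% |
| 20% | 84 | 7.1% | 12.7% |
| 40% | 21 | 2.9% | 5.7% |
| 40% | 84 | 3.3% | 7.6% |

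**Step 5. Effect on the hazard ratio**

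Let f be the share of the control arm's expected risk time in the window, and h the hazard there relative to the rest of control time. Then HR observed = HR true / (1 − f(1 − h)). With an assumed true HR of 0.20, a vaccine effectiveness (VE) of 80%:

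- f = 0.10, h = 0.3: 0.20 / 0.93 = 0.215, VE 78.5%.
- f = 0.10, h = 0.8: 0.20 / 0.98 = 0.204, VE 79.6%.
- f = 0.20, h = 0.3: 0.20 / 0.86 = 0.233, VE 76.7%.
- f = 0.20, h = 0.8: 0.20 / 0.96 = 0.208, VE 79.2%.
- f = 0.40, h = 0.3: 0.20 / 0.72 = 0.278, VE 72.2%.
- f = 0.40, h = 0.8: 0.20 / 0.92 = 0.217, VE 78.3%.

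An f of 0.40 lies well above the person-time shares in step 4. It would need infections concentrated in the window.

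A separate simulation assumed a 35-day interval, completion around July 2021, a summer wave, and hazard ratios against undosed time of 0.5 (partial), 0.3 (window) and 0.2 (complete). It gave HR 0.262 under the text rule and 0.231 with the pair censored at the control's final dose. That is VE 73.8% against 76.9%, a gap of 3.1 points.

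**The case against.** **Table 1 may be using shorthand.** The same cell glosses newly vaccinated people as those completing a primary schedule, and the Statistical analysis plan section does likewise. Table 1 also writes of unvaccinated controls in its booster item, where the text lists name partially vaccinated controls too. The Statistical analysis plan section expects controls to take a first or second dose later. This stands as a likely reading of intent. But the next item in the same list uses the fuller term for the partner, so the plain wording describes two events and needs correcting either way.

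**The 14-day window follows from a declared definition.** People in it have not completed the schedule as the protocol defines completion. This also stands: the rule does not contradict itself. It conflicts with the description of the comparator.

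**The harms do not add up in one analysis.** The vaccination asymmetry belongs to Table 1 read literally, and follow-up of controls after their final dose belongs mainly to the text lists. Only the selection of already fully dosed controls occurs under both.

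**A reader might infer that sites would code different rules and that unlike contrasts would then be pooled.** The protocol does not support this. Under Treatment of personal data, one analytical pipeline developed by the coordination hub is run at every site. What remains is that whoever writes the pipeline has two rules and no stated precedence. That one choice reaches every site, the pooled hazard ratio, and the brand analyses that reuse the same pairs.

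**Conclusion.** The mismatch between the three lists is certain, for both the control's vaccination event and the partner's death. The unpaired partner time (14 days, or the dose interval plus 14 days) holds only if Table 1 is taken literally. A reader might go further and infer a definite bias of the hazard ratio from that asymmetry. The documents give no epidemic curve, dose intervals or uptake by date, so neither its direction nor its size can be supported.

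The selection of fully dosed controls follows directly from the definitions. It moves the estimate towards no effect provided the hazard in the window is below that of other control time (h < 1); with h = 1 there would be no dilution. The amount cannot be derived from the documents. In the central illustrations it is about 1 to 3 points of VE, and it is larger only if the window holds a large share of the control arm's risk. This should be corrected before the analysis is run, but it does not undermine the design.

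**What to change.** 1. Put one identical list of end-of-follow-up events in Table 1, the paragraph on the sequential emulation, and the Statistical analysis plan section.
2. In Table 1, replace the item on vaccination of unvaccinated controls with the same event that censors the partner, for unvaccinated and partially vaccinated controls alike.
3. State the partner-death rule in all three places, for both members of the pair.
4. To match the stated comparator, require that a control has not received the final dose by t0, and censor both members on the date the control receives it. Keep the 14-day lag only for entry to the vaccine group.

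The cost is protocol wording and a dose date that the vaccination registry already supplies. The price in data is slightly fewer controls, less pair follow-up, and days 0 to 13 after the final dose falling in neither arm.
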